1. Medication Administration. Participants will be administered 40 IUs of oxytocin nasal spray or matching placebo at 40 minutes prior to study tasks. This dose was selected based on previous studies that have used similar doses of oxytocin (Ditzen et al., 2009; Heinrichs et al., 2003; Kubzansky et al., 2009), as well as our own previous pilot work (see Preliminary Data). Timing of administration is also based on our pilot work and previous studies showing central activity of oxytocin 40 minutes after intranasal administration (Heinrichs et al., 2009). Intranasal oxytocin and matching placebo will be compounded by a MUSC Investigational Drug Service. Randomization will be done by the MUSC Investigational Drug Service, who will keep a record of the blind and be available should unblinding be required. To achieve balance in sample size with respect to gender, a block randomized design with randomly varying block sizes will be used.

2. TSST. The TSST is a standardized psychological stress challenge which has been used extensively in research studies. A meta-analysis supports its utility for evoking a HPA axis stress response in a laboratory setting (Dickerson & Kemeny, 2004). It has induced a robust and reliable physiological stress response in cocaine, marijuana, and alcohol-dependent individuals in our previous studies (McRae et al., 2006; [name] et al., 2011; Waldrop et al., 2010). When the TSST begins, The participant will be told that (s)he will give a speech and perform an arithmetic task. The topic of the speech will be why (s)he should be hired for a particular job (the individual's "dream job"). The participant will deliver the speech as though speaking to a group of potential employers. The experimenter then tells the participant that (s)he has 5 minutes to prepare the speech, and starts the countdown clock (placed in view of the individual). The experimenter leaves the room to allow the participant to prepare. After 5 minutes, three individuals unfamiliar to the participant (the audience) enter the room and are seated; the individual will be instructed by one audience member to stand

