**C.2.d. Statistical Methods.** The hypotheses associated with Aim 1 are interested in the effect of oxytocin on cocaine craving and stress in response to the TSST. It is hypothesized that cocaine-dependent participants receiving oxytocin will demonstrate greater attenuation of stress and craving response to TSST as compared to those receiving matched placebo. A linear mixed effects model containing all serially measured time points will be used to assess the effects of oxytocin versus placebo on each dependent variable. Restricted maximum likelihood (REML; Patterson and Thompson, 1971) methods will be used to estimate the fixed effects and variance components, and baseline values will be used as covariates in the regression models. To test the hypothesis that women will experience greater ameliorative effects of oxytocin on stress and craving response following the TSST as compared to males, similar models will examine the differential (interaction) in the scores reported between men and women by treatment group (oxytocin vs. placebo). Additionally, as an exploratory analysis, the strength of the effects of oxytocin in women will be assessed with differences in estrogen and menstrual cycle phase as independent variables. In a subgroup analysis of women entered into the study, linear mixed effects models will be developed to assess the association of estrogen and menstrual phase (independently) on the stress and craving response to the TSST. Non-linear associations will also be explored using cubic spline models (Marrie et al., 2009). Within each family of dependent measures, the Type I error rate will be controlled using a post-hoc Bonferroni correction.

The hypotheses associated with Aim 2 are concerned with the impact of oxytocin on cocaine cue reactivity. It is hypothesized that oxytocin will decrease cue-induced cocaine craving in cocaine-dependent men and women compared with placebo administration. Post-acquisition preprocessing and statistical analysis will be performed using Matlab 7.8 (Mathworks, Sherborn, MA) with Statistical Parametric Mapping software 8

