**C.2.e. Power and Sample Size.** *Aim 1.* It is hypothesized that oxytocin will decrease ratings of subjective stress and cocaine craving following the TSST relative to placebo. Pilot data suggests an expected between group mean differences in total cocaine craving (CCQ) following the TSST of  $\Delta = 8.24$  with a RMSE = 11.03 ( $d = 0.75$ ) (Cohen, 1988) and a stress rating (VAS) difference of  $\Delta = 1.07$  with a RMSE = 2.20 ( $d = 0.49$ ). As in the oxytocin pilot study, participants will be assessed at four post TSST time points ( $m$ ), with an anticipated intraclass correlation coefficient of 0.78 for both craving and stress outcomes (ICC = 0.78 & 0.79, respectively). The design effect, which accounts for the multiple correlated observation within each subject, is estimated to be 3.35 (DE =  $[1 + (4-1)0.78]$ ) (Donner and Klar, 2000). Assuming independent observations and an effect similar to the pilot data for the stress response ( $d = 0.48$ ), the total effective sample size would be 140 subjects (35 men and 35 women per treatment arm) to provide 80% power with a type I error rate of 0.05. In a clustered setting, the sample size is  $N_{\text{effective}} = nm/DE$  where  $n$  is the number of participants required when  $m$  replications within participants are performed after accounting for the design effect (DE). For the study at hand, the total

Version 16.0 (Revised 08/01/2016)

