number of participants required is therefore estimated to be  $n=118$  ( $=140 \times 3.35/4$ ), which will be rounded to 120 to provide balance with respect to gender. Given an expected retention rate of approximately 80%, we will recruit 152 participants to obtain a final sample size of 120. This sample size will provide adequate power (80%) to detect the planned stress response, and more than adequate (98%) to detect the planned craving response to the TSST. In addition, the sample size of 120 participants will also provide 80% power to detect a 1 standard deviation differential in treatment effect between cocaine-dependent men and women for the craving response to the TSST. *Aim 2.* Existing fMRI studies involving cocaine cue exposure have included between 6 (Maas et al., 1998) and 17 (Garavan et al., 2000) participants per group, and have reliably found activation in brain regions associated with cocaine craving (e.g., anterior cingulate, amygdala). However, Mumford & Nichols (2008) simulation study suggested that 23 participants per group may be necessary to obtain 80% power for a generic fMRI task design featuring 10, 15-second task block and 10, 15-second rest blocks. As such, our proposed 60 completers participants per group should provide adequate statistical power.

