### 5.1 Summary of the Protocol.

This application proposes to investigate the effects of oxytocin on stress and cue induced reactivity in cocaine-dependent individuals, and whether gender differences in response exist. The primary outcome of interest is craving and stress response to the interventions. Inclusion/exclusion criteria are outlined above. Power calculations and sample sizes are in the Data Analysis Plan section above.

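### The Hypothesis 1a model does not name sex, although randomisation balances on it; adding it costs almost nothing and may recover a little power for the stress outcome (minor)

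*Combined protocol and SAP*

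**What the plan says.** Section C.2.d (Statistical Methods) sets out the Aim 1 analysis in a few sentences.

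- For the effect of oxytocin on each outcome (Hypothesis 1a), a "linear mixed effects model containing all serially measured time points will be used to assess the effects of oxytocin versus placebo".
- On covariates: "baseline values will be used as covariates in the regression models". No other covariate is named.
- Sex enters at the next step, for Hypothesis 1b, where "similar models will examine the differential (interaction) in the scores reported between men and women by treatment group".
- On multiplicity: "Within each family of dependent measures, the Type I error rate will be controlled using a post-hoc Bonferroni correction". The size of the family is not given.

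Elsewhere sex is part of the design. Under Medication Administration in C.2.c.2: "To achieve balance in sample size with respect to gender, a block randomized design with randomly varying block sizes will be used". Section C.2.e counts the effective sample as "35 men and 35 women per treatment arm" and rounds the completers to 120 to keep the sexes balanced. It claims "adequate power (80%) to detect the planned stress response, and more than adequate (98%) to detect the planned craving response". Section 5.1 treats both outcomes as primary: "The primary outcome of interest is craving and stress response to the interventions".

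**The concern.** A factor used to balance the randomisation is normally also a term in the analysis. Here it is absent from the one model that tests the main effect of oxytocin on the two primary outcomes. Section C.1.a reports, in general terms, that cocaine-dependent women respond more strongly to stress than men. The connectivity analysis for Exploratory Hypothesis 2d does carry gender alongside treatment, so its absence from 1a stands out.

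If men and women differ on post-task scores after baseline adjustment, that difference goes into the residual. With allocation balanced within sex, the true standard error of the oxytocin effect does not change but the model overstates it, so the test is conservative. With sex left to chance, imbalance between arms adds real variance. In both cases the cost is power. Stress is the outcome that set the sample size, and it has only about two points of margin over 80%.

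**Working it through.** **Inputs from C.2.e.** Stress d = 0.48 (1.07/2.20 = 0.486); craving d = 0.75 (8.24/11.03); 4 post-task measurements; ICC 0.78 (0.79 for stress, an immaterial difference); 120 completers; α = 0.05, taken as two-sided.

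**Assumed, because the documents do not give it.** The sex difference remaining after baseline, δ = 0.2, 0.3, 0.5 or 0.8 SD of the subject mean, with men and women in equal numbers.

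**The plan's own figures.** A two-sided t-test at d = 0.48 with 70 per arm has 80.5% power, so 140 effective subjects reproduces. Then 140 × 3.35/4 = 117.25, rounded up to 118 and then to 120.

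**Power at 120 completers, sex in the model.**
- Variance of a subject mean, in single-observation units: (1 + 3 × 0.78)/4 = 0.835.
- Noncentrality = d/√0.835 × √(120/4): 2.877 for stress and 4.496 for craving.
- Power = Φ(2.877 − 1.96) = 82.0% and Φ(4.496 − 1.96) = 99.4%. The plan states 80% and 98%.

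**Sex omitted, allocation balanced within sex, RMSE taken as free of sex variance.** The estimated SE is too large by r = √(1 + δ²/4). Power = Φ(noncentrality − 1.96r); type I error = 2(1 − Φ(1.96r)).

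| δ (SD) | r | Type I error | Stress power (82.0% with sex) | Craving power (99.4% with sex) |
|---|---|---|---|---|
| 0.2 | 1.005 | 0.049 | 81.8% | 99.4% |
| 0.3 | 1.011 | 0.048 | 81.5% | 99.4% |
| 0.5 | 1.031 | 0.043 | 80.4% | 99.3% |
| 0.8 | 1.077 | 0.035 | 77.8% | 99.1% |

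Simulation on subject means (40,000 runs per setting, t critical values, 30 per cell) gives stress power without sex of 0.808, 0.807, 0.794 and 0.771, against 0.810 to 0.814 with sex. Bias is at most 0.001.

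**Where stress power crosses 80%.** The normal approximation gives δ = 0.56. With t critical values it is about 0.46, because power with sex in the model then starts at 81.4%. In scale units, 0.46 × √0.835 × 2.20 ≈ 0.92, not far below the planned oxytocin effect of 1.07.

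**Sex omitted, blocks not formed within sex (simulation).** Type I error is 0.048 to 0.050. Stress power without v with sex is 0.812 v 0.812, 0.808 v 0.814, 0.788 v 0.809 and 0.756 v 0.812 at the four values of δ. The largest loss is 0.812 − 0.756 = 0.056.

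**If the RMSE of 2.20 already contains sex variance (balanced within sex).** The true noncentrality becomes 2.877r. Power without sex = Φ(r(2.877 − 1.96)); power with sex = Φ(2.877r − 1.96).
- δ = 0.2: Φ(0.922) = 82.2% without, Φ(0.931) = 82.4% with.
- δ = 0.8: Φ(0.988) = 83.8% without, Φ(1.139) = 87.3% with.

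**Bonferroni, assuming a family of two (α = 0.025, z = 2.241).** Stress power is 73.8% with sex. Without it, power is 73.4% at 0.2 SD and 67.8% at 0.8 SD. Craving goes from 98.8% to 98.1% at 0.8 SD.

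**Cost if sex does not predict the outcome.** Simulated stress power is 0.811 with or without sex when allocation is balanced within sex, and 0.809 without v 0.813 with sex when it is not.

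**The case against.** The strongest reply is that nothing here is wrong. The 1a model is valid as written, and the point rests on silence in a short paragraph that does not list every fixed effect. A sex-by-treatment model for 1b would ordinarily carry the sex main effect, so a sex-adjusted oxytocin contrast is within reach of a planned analysis. This stands in part: the plan does not exclude sex. But it does not say that the 1a result will be taken from the 1b model either, and one sentence would settle it.

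A second reply is that the harm depends on an unknown. The statement in C.1.a about women's stronger response is general. The specific results around it concern correlations between ratings and the hormonal response to CRH, not a mean sex difference in post-TSST stress ratings after baseline. This stands, which is why the loss is shown as a range that starts from nothing.

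A third reply is that the pilot RMSE may come from a model without sex. If so, the planned 80% already absorbs the omission. This also stands, and it limits what can be said about falling short of plan.

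A reader might go further and infer that the 1a test is biased or invalid, that its type I error is necessarily below 0.05, or that the trial is underpowered for stress. The documents support none of these. The estimate is unbiased under either allocation scheme. The conservatism needs allocation balanced within sex, which the randomisation text does not state. A shortfall needs both a sizeable remaining sex difference and an RMSE free of sex variance.

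**Conclusion.** The point holds as a free improvement of minor severity. The 1a model omits the factor on which the trial balances its randomisation; the test remains valid.

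- If sex predicts stress after baseline by 0.2 to 0.8 SD of the subject mean (assumed), leaving it out costs about 0.3 to 4 points of power with allocation balanced within sex, and up to about 6 points otherwise.
- Craving loses less than half a point in the balanced case. If sex is not prognostic, nothing is lost on either outcome.
- If the pilot RMSE excludes sex variance and allocation is balanced within sex, stress power drops below 80% once the remaining difference exceeds roughly 0.46 SD with t critical values (0.56 SD by the normal approximation).
- If the RMSE already includes sex variance, power without sex stays at about 82 to 84%, and adding sex raises it to about 82 to 87%.

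That sex is unnamed, and that adding it is nearly free, is certain. The size of the gain is not, because the documents give neither the remaining sex difference nor the content of the pilot model.

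**What to change.** In C.2.d, name sex as a main-effect covariate in the Hypothesis 1a models for craving and stress. If the 1a effect is meant to come from the 1b model, say so and define the contrast. In the randomisation text, state whether blocks are formed within sex. It would also help to say in C.2.e whether the pilot model behind the RMSE of 2.20 included sex.

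The cost is a line or two of text and one degree of freedom out of about 117. Sex is already recorded, and the sample size does not change. Fixing the covariate before unblinding also removes a modelling choice that would otherwise be left open.

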**Title: Oxytocin in Cocaine Dependence**

**NCT: 01573273**

**Date of Document: 8/1/2016**

## Oxytocin in Cocaine Dependence

### SPECIFIC AIMS

Previous work conducted by the MUSC SCOR identified sex/gender differences in preclinical and clinical models of cocaine cue and stress reactivity that may contribute to gender differences in relapse. The proposed project will build on this work by exploring potential mechanisms for these sex/gender differences. Specifically, several studies have indicated that hypothalamic neuropeptides mediate behavioral responding to stress as well as play a role in neuroadaptations that occur as a consequence of long-term cocaine use. The hypothalamic neuropeptide oxytocin promotes trust, social bonding, and calmness. Given these effects, oxytocin may have a therapeutic role in ameliorating the negative affect commonly observed prior to relapse in cocaine-dependent individuals. As estrogen appears to enhance oxytocin's effects, women may have an enhanced response to oxytocin. The specific aims of the proposed project are:

**Specific Aim 1: Using a human laboratory paradigm, determine the impact of oxytocin on stress-induced craving in cocaine-dependent women and men.**

Preclinical and clinical investigations have found that the neuropeptide oxytocin exerts anxiolytic effects in stress paradigms. However, little is known about the potential anxiolytic effects of oxytocin in cocaine-dependent individuals, or if a gender differential in response exists.

**Hypothesis 1a:** Intranasal administration of oxytocin will attenuate drug craving response and stress reactivity to a psychosocial stress task in cocaine-dependent individuals compared to placebo administration.

**Hypothesis 1b:** The ameliorative effects of oxytocin on drug craving response and stress reactivity will be more pronounced in cocaine-dependent women as compared to cocaine-dependent men.

**Exploratory Hypothesis 1c:** The stress and craving reduction induced by oxytocin in women will be related to estrogen and progesterone levels.

**Specific Aim 2: Using a neuroimaging cue paradigm, explore the impact of oxytocin on neural correlates and subjective responses of cocaine cue reactivity in cocaine-dependent men and women.**

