**Impact of estrogen and progesterone on reward, craving, and response to oxytocin.** Estrogen and progesterone levels fluctuate throughout the menstrual cycle. Progesterone levels peak seven to twelve days after ovulation marking the middle of the luteal phase; estrogen levels dominate throughout the cycle but peak six to ten days after the start of the menstrual cycle, marking the mid-follicular phase (Evans et al., 2002). In addition to sex differences in brain structure, function, and neurochemistry, circulating gonadal hormones play a critical role in mediating the subjective response to the drug itself, cues, and stress. Preclinical studies have localized estrogen and progesterone receptors to brain regions responsible for mediating the physiological and behavioral response to stress and cues (Alves et al., 1998; Cushing & Kramer, 2005; Laflamme et al., 1998). Preclinical studies conducted by MUSC SCOR investigators demonstrated that cocaine seeking is significantly attenuated during the proestrus phase of the estrous cycle when progesterone levels are highest (Feltenstein & See, 2007; Kippin et al., 2005). In a recent study of treatment-seeking cocaine-dependent women, subjective craving following exposure to a laboratory stressor was significantly lower in women with elevated progesterone compared to women with low progesterone (Sinha, et al., 2007). It has also been demonstrated that ovarian hormone levels can impact the response to smoked cocaine with the positive or “rewarding” effects of cocaine significantly lower during the luteal phase compared to the follicular phase (Evans et al., 2002; Sofuoglu et al., 1999). Taken together, these studies indicate that during the follicular phase when estrogen levels are elevated, the positive and rewarding properties of stimulants peak, while increases in progesterone during the luteal phase may decrease craving and/or drug effect.

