the SCID-I/P (Sheehan & Lecrubier, 2003; Sheehan et al., 1998). **Structured Clinical Interview for DSM-IV (SCID-I/P)**: The SCID-P is a structured diagnostic interview that assesses each of the criteria for DSM-IV diagnoses. The alcohol and drug use disorder modules will be to thoroughly assess both current and lifetime diagnostic status for abuse and dependence. It has excellent inter-rater and test-retest reliability (First et al., 2002). **Menstrual History Diary**: Participants will be asked to estimate the timing of their cycle for the 90-days prior to study entry and to track their cycle during study participation. **Daily Hassles Scale**: The Daily Hassles Scale consists of a list of 117 irritating, frustrating, or distressing events that characterize everyday interactions with the environment. Participants rate both frequency and intensity for the past month. The Daily Hassles Scale is positively correlated with adaptational ability and is a good predictor of psychological symptoms (Kanner et al., 1981). **Adverse Childhood Experiences (ACE) Questionnaire**: The modified ACE questionnaire assesses childhood maltreatment and exposure to household dysfunction. It has been utilized to examine the relationship between adverse childhood experiences and health risk behavior in adulthood (Felitti et al., 1998). In addition to providing data to assess the impact of early childhood trauma on cocaine use, utilization of the ACE will allow for potential cross-SCOR collaborations as it also being employed by the UCLA, Yale and Harvard SCORs. **Childhood Trauma Questionnaire (CTQ)**: The CTQ is a 25-item self-report questionnaire used to assess the extent to which individuals have experienced five domains of childhood abuse and neglect (sexual abuse, physical abuse, emotional abuse, emotional neglect and physical neglect). Subjects answer each question using a 5-point Likert scale ranging from (1) never true to 5 (very often true). Severity scores for each domain can range from 5 (no history of abuse/neglect) to 25 (severe abuse/neglect). The questionnaire also includes a minimization/denial scale. The reliability and validity of the CTQ are excellent (D. P. Bernstein, et al., 1997; D. P. Bernstein, Fink, L.A., 1998). The **Pittsburg Sleep Quality Index** will be used to assess sleep patterns (Buysse, et al., 1989). The **Quick Inventory of Depressive Symptoms** (Rush, et al., 2003) will be used to measure depression and a short form anxiety scale from the PROMIS© item bank will be used to measure anxiety. The **Life Events Occurrence Scale** (Maciejewski, et al.) will be used to inventory adult trauma. A brief survey from the National Health and Nutrition Examination Survey (CDC, 2000) will be used to rate quality of life, and a body map will be used to rate areas of pain. A brief smoking history will also be obtained.

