
**b. Substance-Related Instruments. Form 90**: The Form 90 (Miller, 1996), an assessment instrument commonly used in substance use studies, is similar in concept to the Time Line Follow-back (Sobell & Sobell, 1992). This is a calendar-based instrument designed to assess daily substance consumption. Study participants will be asked to estimate the amount of substance consumed with the aid of visual cues designed to accurately quantify consumption. Cocaine will be recorded in dollar value, as well as quantity, in order to standardize for different types of cocaine use (crack, IV, nasal, etc.). Alcohol, nicotine, and other drug use will also be tracked. For cocaine use, the data will be summarized in three ways: a) percent of abstinent days (i.e., no use), b) amount of use per day, and c) amount used per using day **Inventory of Drug-Taking Situations (IDTS)** (Annis et al., 1997): This instrument measures typical drug using situations based on Marlatt and Gordon's (1985) eight category taxonomy. This instrument contains eight subscales mapping frequency of use in eight distinct types of situations including use during negative situations (unpleasant emotions) and positive situations (social situations). Although initially calculated to assess alcohol use, this scale has been modified for use with drug abusers and has demonstrated sensitivity to gender differences (Ross et al., 1994). Participants will also be asked to provide a urine sample to be tested for drugs of abuse.

**c. Progesterone and Estrogen Tracking**. We will explore the impact of progesterone and estrogen levels on cocaine craving, stress, and oxytocin effects. Because our hypotheses are related to ovarian hormone levels rather than menstrual cycle phase, direct measurement of hormone levels at the time of testing is the most appropriate measure to address our hypotheses (Becker et al., 2005). As there is significant individual variability in progesterone and estrogen levels across the menstrual cycle, we will measure progesterone and estrogen at the initial assessment and each of the three study visits. We expect that these four samples will provide a profile of hormone levels for each study participant. Since we are interested in having a range of hormone levels for comparison, we will test 50% of participants during the luteal phase when progesterone

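### The stated model for exploratory Hypothesis 1c uses estrogen and menstrual phase and leaves out the progesterone level, which the hypothesis names and the trial measures

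*Combined protocol and SAP*

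**What the plan says.** Specific Aims, Exploratory Hypothesis 1c: "The stress and craving reduction induced by oxytocin in women will be related to estrogen and progesterone levels".

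The Progesterone and Estrogen Tracking paragraph of C.2.c.1 sets the purpose: "We will explore the impact of progesterone and estrogen levels on cocaine craving, stress, and oxytocin effects". It then gives the reason for assaying hormones: "Because our hypotheses are related to ovarian hormone levels rather than menstrual cycle phase, direct measurement of hormone levels at the time of testing" is called the most appropriate measure. It cites individual variability in both hormones, plans four samples per participant, and ends by saying that absolute levels of both will be used as continuous measures. Phase is approximated from a menstrual history so that visits can be scheduled half in the luteal and half in the follicular phase. The diary entry reads: "Participants will be asked to estimate the timing of their cycle for the 90-days prior to study entry and to track their cycle".

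Session Preparation (C.2.c.2.a) collects salivary progesterone and estradiol at baseline on the test day, and the Assessments paragraph describes both assays.

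C.2.d Statistical Methods gives the analysis in two sentences. One says "the strength of the effects of oxytocin in women will be assessed with differences in estrogen and menstrual cycle phase as independent variables". The next describes mixed models in women to "assess the association of estrogen and menstrual phase (independently) on the stress and craving response to the TSST". Neither names progesterone, and the word does not occur elsewhere in C.2.d or in the power section, C.2.e.

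**The concern.** An analyst who follows C.2.d would fit estrogen and phase. The progesterone level, one of the two modifiers named in 1c, would be collected and assayed but would have no place in the stated model. The Significance section gives progesterone a role in this population: in a cited study of cocaine-dependent women, "subjective craving following exposure to a laboratory stressor was significantly lower in women with elevated progesterone compared to women with low progesterone".

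A smaller point concerns the form of the test. Hypothesis 1c is about effect modification, which calls for a treatment-by-hormone term. The first sentence in C.2.d implies this. The second describes only an association with the TSST response, which may be meant for the separate question of hormones and craving. For Hypothesis 1b the same paragraph writes the word interaction; for 1c it does not. A hormone main effect could therefore be reported as support for 1c.

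**Working it through.** **Text comparison**

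| Place | Predictors | Form |
|---|---|---|
| Hypothesis 1c | estrogen, progesterone | levels |
| C.2.c.1, hormone tracking | estrogen, progesterone | continuous levels, preferred to phase |
| C.2.c.2.a and Assessments | estradiol, progesterone | salivary, test day |
| C.2.d, first sentence | estrogen, phase | not stated |
| C.2.d, second sentence | estrogen, phase, each separately | cubic splines to be explored |

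Estrogen is carried through; progesterone is replaced by phase. A two-level phase variable also cannot carry the planned cubic spline, so the non-linear exploration is unavailable for progesterone as written.

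**Illustrative cost of the substitution.** The plan gives no power figure for 1c, so there is none to reproduce.

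Inputs from C.2.e: 120 completers, half of them women, so 60 women and 30 per arm; four post-task ratings; ICC 0.78; RMSE 11.03 (CCQ) and 2.20 (VAS), read here as the SD of one rating. From Assessments: saliva-serum correlation for progesterone 0.80.

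Assumptions not in the documents: normally distributed hormone; the slope; the correlation between phase and level; the slope difference split equally between arms; no gain from baseline adjustment.

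1. SD of a participant's four-rating mean, in units of one rating's SD: √[(1 + 3 × 0.78)/4] = √0.835 = 0.914.
2. Model: mean response on arm, hormone and arm × hormone, with a two-sided t-test on 60 − 4 = 56 df. Simulation gives a type I error of about 5%. Power is about 80% for a change in the oxytocin effect of 0.70 to 0.71 SD per SD of hormone.
3. On the outcome scales, 0.70 × 11.03 = 7.7 CCQ points and 0.70 × 2.20 = 1.54 VAS points. The planned overall effects are 8.24 and 1.07.
4. Replace the level by phase (15 luteal and 15 follicular per arm, slope 0.71):

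| Correlation of phase with level (assumed) | 0.5 | 0.6 | 0.7 | 0.8 | 0.9 |
|---|---|---|---|---|---|
| Power using phase | 29% | 40% | 51% | 64% | 75% |
| Power using the level, same trials | 81–83% | 81–83% | 81–83% | 81–83% | 81–83% |

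5. If the serum level is what matters and saliva correlates 0.80 with it, the salivary level has about 60–63% power. Phase matches that only if its own correlation with serum is about 0.8 or more.
6. With the whole slope in the oxytocin arm, phase power is 1 to 3 points lower (about 27% at 0.5 and 73% at 0.9).
7. At half the slope (0.35), the level has about 30% power and phase about 11% to 26% for correlations of 0.5 to 0.9.

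**The case against.** The strongest reply has four parts.

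- **Phase stands for progesterone, and the intent to use levels is already stated.** The hormone-tracking section does describe luteal as high and follicular as low, and it promises continuous levels of both hormones. Phase is also a scheduling factor, so a model that includes it is defensible. But that section gives no outcome, model or interaction term, and C.2.d gives a model that differs from it. In the hormone section, phase is approximated from a history, and a visit moved after a positive drug screen may fall in another phase. C.2.d does not say how phase is assigned for analysis. The two sections need reconciling whichever governs.
- **The Significance evidence on progesterone concerns craving, not the oxytocin effect.** This stands. The documents' rationale for a stronger response to oxytocin rests on estrogen. Hypothesis 1c nevertheless names progesterone as a modifier.
- **The power figures are mostly assumption.** This also stands. A slope of 0.71 is close to the whole planned craving effect and larger than the planned stress effect. At smaller slopes neither analysis is informative, and under the serum scenario phase can equal or beat saliva. The figures illustrate direction and do not measure the defect.
- **1c is exploratory.** It is, and this limits the consequence. It does not explain why one of the two named predictors is missing from the only stated model.

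**Conclusion.** The concern holds. C.2.d replaces a hypothesized and already collected predictor with the variable that the hormone section sets aside. Followed as written, the progesterone half of 1c is never tested on levels. This rests on the text alone.

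The size can only be illustrated: about 80% power on the level against about 29% to 75% on phase, under an assumed slope of 0.71 SD per SD and assumed correlations of 0.5 to 0.9. The missing interaction term is a lesser point, since C.2.d implies it. Hypotheses 1a and 1b and the sample size do not depend on 1c. The correction should be made, but it does not threaten the main Aim 1 analysis.

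**What to change.** In C.2.d:

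- State that 1c is examined in women through treatment × estradiol and treatment × progesterone interactions. Use the session-day salivary levels as continuous predictors, with their main effects and the baseline covariate.
- Keep phase, defined from the menstrual history and diary, as a descriptive or sensitivity variable.
- Say that a hormone main effect answers the separate question on craving and stress and is not support for 1c.
- Fix before unblinding whether levels are log-transformed and whether the hormones are fitted jointly or separately.
- The multiplicity sentence reads "Within each family of dependent measures, the Type I error rate will be controlled using a post-hoc Bonferroni correction". State whether it covers these exploratory tests and with what family size.
- Report estimates with confidence intervals.

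The cost is wording, since both hormones are already collected. The drawback is low precision with about 60 women. One interaction reaches 80% power only at about 0.70 SD per SD of hormone. With Bonferroni over 2, 3 or 5 measures (assumed, as no family size is given), this rises to about 0.78, 0.83 or 0.88 SD. With both hormones fitted jointly and correlated 0.3, 0.5 or 0.7 (assumed), it is about 0.76, 0.83 or 1.01 SD at an unadjusted 0.05. The results should be presented as exploratory.
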